## 7 Interim Analysis

Three interim analyses will be performed in addition to the main analysis. The first will be initiated at the end of enrollment, the second will be initiated at the point all subjects complete 1 year of follow-up, and the third will be initiated at the point all subjects complete three years of follow up. The purpose of these analyses is to formally review study data, at the request of FDA.

The following will be summarized as part of these interim analyses:

1. Demographic information listed in Section 9.3.1.
2. The proportion of subjects reporting AEs of chronic lower abdominal and / or pelvic pain after insertion of Essure System compared to the proportion of subjects reporting AEs of chronic lower abdominal and / or pelvic pain after laparoscopic tubal sterilization.
3. The proportion of subjects reporting AEs of abnormal uterine bleeding after insertion of Essure System compared to the proportion of subjects reporting AEs of abnormal uterine bleeding after laparoscopic tubal sterilization.
4. Proportion of subjects with allergic / hypersensitivity reactions possibly attributed to wearing of Essure devices and allergic / hypersensitivity reactions in women undergoing laparoscopic tubal sterilization.
5. Proportion of subjects with newly diagnosed autoimmune disorders in subjects wearing Essure inserts compared to subjects undergoing laparoscopic tubal sterilization.
6. Proportion of subjects undergoing invasive gynecologic surgery after Essure placement (excluding second placement attempts), including Essure insert removal compared to the proportion of subjects undergoing gynecologic surgery after laparoscopic tubal sterilization.
7. Rates of AEs in subjects undergoing Essure placement and laparoscopic tubal sterilization.
8. The proportion of subjects reporting each protocol deviation.

The propensity score (PS) model will be developed, after all subjects have been enrolled, by an outcome-blinded independent party which will only have access to baseline characteristics and sterilization group. This process may need to be repeated once all subjects complete 3 years of follow-up due to subject drop-out. The first interim analysis will be initiated after the PS matching process has completed. Both interim analyses will be performed on a PS-matched population in order to adjust for measured confounding as well as on the total population. In other words, the main analysis sets are the Adjusted Full Analysis Set (PS-matched population among subjects where a sterilization procedure of choice was attempted) and the Full Analysis Set (sterilization procedure of choice was attempted) for the interim analyses. A Reliance Set will consider women relying on the sterilization method selected at the index event.

For all the outcomes and variables, a descriptive analysis will be performed and no statistical comparison will be made. For continuous data, N, mean, standard deviation, min, and max will be provided and for categorical data, frequency and percentages will be provided. Unless otherwise specified, the analyses will be presented in a way that events will be assigned to the treatment which was given initially at the index event.

Summaries for the interim analyses will use all data up to the data cutoff dates, which will be at the time enrollment ends and at the end of 3 years of follow-up.

Results of the interim analyses will be summarized in a separate report.

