The PS model will be developed, after all subjects have been enrolled, by an outcome-blinded independent party which will only have access to baseline characteristics and sterilization group. Balance of the PS baseline characteristics will be assessed at the 3-year interim analysis and end of study; if necessary, the process will be reevaluated to ensure balance of baseline characteristics throughout the study. The first interim analysis will be initiated after the PS matching process has completed. All 3 interim analyses will be performed on a PS-matched population in order to adjust for measured confounding as well as on the total population. In other words, the main analysis sets are the Adjusted Full Analysis Set (PS-matched population among subjects where a sterilization procedure of choice was

attempted) and the Full Analysis Set (sterilization procedure of choice was attempted) for the interim analyses. A Reliance Set will consider women relying on the sterilization method selected at the index event.

For all the outcomes and variables, a descriptive analysis will be performed and no statistical comparison will be made. For continuous data, N, mean, standard deviation, min, and max will be provided and for categorical data, frequency and percentages will be provided. Unless otherwise specified, the analyses will be presented in a way that events will be assigned to the treatment which was given initially at the index event.

Summaries for the interim analyses will use all data up to the data cutoff dates, which will be at the time enrollment ends, after all subjects complete 1 year of follow-up, and at the end of 3 years of follow-up. Serology data (cytokines, nickel and titanium levels, and nickel LPT results) will be summarized in the interim analysis to be performed at the end of 3 years of follow-up. The interim analysis report will also include a description of the pathologic and histologic findings of fallopian tubes, and individual dossiers provided to the Adjudication Committee in cases of potential hypersensitivity/allergy/autoimmune reactions.

Results of each interim analysis will be summarized in a separate report.

The interim analysis reports will be submitted no later than 3 months after database lock for each interim analysis data cutoff date.

11. Interim and final post market surveillance report

Section added by Amendment 2 (Modification 26). Section modified by Amendment 4 (Modification 1)

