### **4.3 Handling of loss to follow-up, premature discontinuation, and censoring**

Subjects who leave the study before reaching the study completion assessment five years after start of the sterilization procedure will be included in the analysis populations, since the analyses are based on all subjects who attempt sterilization.

For subjects who attempt two sterilization methods, or have any hysterectomy (subtotal, total or radical), or have Essure complete removal using a salpingectomy, or device removal not accompanied by sterilization procedure, their data will be censored for analysis purpose on the earliest date of second sterilization method, hysterectomy surgery date, or Essure removal date, for the primary analysis.

Data will be collected for all the subjects until the end of study or early termination.

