## **4.5 Interim analyses and data monitoring**

### **4.5.1 Interim and final post market surveillance report**

Bayer will submit an Interim Postmarket Surveillance Report every 6 months for the first 2 years of the postmarket surveillance and annually, thereafter, from the date of approval of the 522 postmarket surveillance study plan which was anticipated to be on September 4, 2016.

Per FDA's final guidance document on Postmarket Surveillance issued on May 16, 2016 (located at <http://www.fda.gov/downloads/MedicalDevices/DeviceRegulationandGuidance/GuidanceDocuments/ucm268141.pdf>), after approval of the study plan, FDA may post surveillance plan parameters related to the study design and objectives on the FDA postmarket surveillance webpage (<http://www.accessdata.fda.gov/scripts/cdrh/cfdocs/cfPMA/pss.cfm>). Furthermore, the FDA may post the following information from interim postmarket surveillance reports in the following conditions:

- Number of study sites enrolled (to be updated after submission of each interim report).
- Number of patients enrolled (to be updated after submission of each interim report).
- Interim summary data and/or analyses thereof when appropriate to protect the public health, for example when interim results raise safety concerns or may otherwise impact treatment.
- Interim summary data and/or analyses thereof when statistically and methodologically appropriate and mutually agreed upon by FDA and Bayer, to be negotiated at such time.

The final post market surveillance report will be submitted no later than three months after postmarket surveillance study completion (as defined by database lock).

When recruitment is finalized, the Propensity Score (PS) development will start. For this purpose, an outcome-blinded party independent to the conduct of the study will receive all baseline data of subjects together with their initial treatment allocation (at index).

The independent party will generate a proposal to proceed on the basis of the data available. This will also include assessments on the overlap of the PS density functions for the treatments, and its impact on the adequacy of analyses planned. The generation of the score will be documented with all decisions taken (variables selected for inclusion in the model, procedures to achieve balance, (matching procedures (caliper distance) and final model).

This proposal will subsequently be discussed with the FDA.

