## **5 Analysis sets**

### **5.1 Assignment of analysis sets**

The goal of this study is to assess the various aspects of safety of the procedures studied. Assuming there is adequate overlap in the PS distribution to enable comparisons in the PS confounder-adjusted population between treatment groups, the adjusted full analysis set will be the primary analysis set.

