### 6.6.1 Development of propensity score

In order to assure that the PS is developed without knowing any outcome variables, the iterative model build process will be conducted by an outcome-blinded independent party which has only access to the treatment variable and the baseline variables listed in [Table 2](#).

The outcome variables will be removed from the data set during PS development; those constructing the score will not have access to any outcome information. Any variable measured after the treatment decision will be considered an outcome, as it could have been affected by the treatment.

The initial sterilization treatment will be considered the “treatment” for the purpose of the PS analyses.

All baseline variables will be considered for inclusion into the model; however the variables in [Table 5](#) have shown previous evidence to likely be included in the model. The decision to keep them or to remove them from the model or to alter the level of scale will be decided during the build of the score using analysis diagnostics as described below. A detailed report on the procedures applied for selection of variables and for considerations for analyses will be provided by the independent party.

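### Repeating the propensity-score match after 3 years because of drop-out, with no rule on who is matched, could make the primary analysis set depend on who stayed in the study

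*SAP*

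**What the plan says.** SAP 7 has the propensity score developed after enrollment closes by an "outcome-blinded independent party which will only have access to baseline characteristics and sterilization group". Matching must be complete before the first interim analysis. The SAP then adds: "This process may need to be repeated once all subjects complete 3 years of follow-up due to subject drop-out". It sets no balance threshold, does not define the pool for a repeat match, and does not order the repeat relative to the 3-year interim.

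Protocol 10.5 (version 5.0, repeated in the synopsis) says "Balance of the PS baseline characteristics will be assessed at the 3-year interim analysis and end of study", and "if necessary, the process will be reevaluated to ensure balance of baseline characteristics throughout the study". It does not give drop-out as the reason. SAP 1.2 lists protocol versions only up to Amendment 3, whereas the balance check came in with Amendment 4.

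Three other SAP statements bear on this:

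- SAP 5.1, provided the score distributions overlap adequately: "the adjusted full analysis set will be the primary analysis set".
- SAP 6.6.1, on what the matching party may use: "Any variable measured after the treatment decision will be considered an outcome, as it could have been affected by the treatment".
- SAP 4.3, on women who leave before five years: they "will be included in the analysis populations, since the analyses are based on all subjects who attempt sterilization".

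**The concern.** Matching on baseline covariates is protected from outcome-driven selection only if the matched set is fixed by information available at the procedure. A repeat match prompted by drop-out appears to replace that set with one built from women still in follow-up. Staying in follow-up happens after treatment and may be related to pain, bleeding or surgery. A woman who leaves such a set takes with her any events already recorded.

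What is at stake is the main confounder-adjusted comparison. It could carry a selection bias that baseline balance tables do not show. It could also rest on different women in the final report than in the end-of-enrollment and 1-year interim reports, both of which summarize the main endpoints by group.

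**Working it through.** The plan states no sample size, event rate or drop-out rate, so there is no figure of its own to reproduce. The check has a logical part and an illustrative part.

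**Can drop-out change the match without selecting on retention?**

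1. FAS membership is decided at the procedure: device introduced into the hysteroscope, or skin incised or punctured (SAP 5.1).
2. Baseline is the last value at or before the index event (SAP 4.6.1).
3. Treatment for the score is the initial sterilization procedure (SAP 6.6.1).
4. None of these changes when a woman leaves. The same procedure run again on the whole FAS therefore has the same inputs. In simulation, re-running a deterministic 1:1 nearest-neighbor match (caliper 0.2 SD of the logit score) on unchanged data returned identical pairs in every run.
5. So drop-out can alter the match only if retention status decides who enters it. By SAP 6.6.1's own rule retention counts as an outcome, and by SAP 4.3 leavers are supposed to stay in.

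**How large could the effect be?** All rates here are assumptions. Let the true risk p be equal in both arms, d1 be drop-out among women with the event and d0 drop-out among women without it. Risk among those retained is

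p(1 − d1) / [p(1 − d1) + (1 − p)(1 − d0)].

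Take p = 20%, with 20% drop-out in all laparoscopic women and in event-free Essure women. Laparoscopic arm: 0.16/(0.16 + 0.64) = 20.0%. Essure arm:

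| Drop-out, Essure women with event | Calculation | Retained risk | Difference (points) |
|---|---|---|---|
| 10% | 0.18/(0.18 + 0.64) | 22.0% | +2.0 |
| 20% | 0.16/(0.16 + 0.64) | 20.0% | 0.0 |
| 30% | 0.14/(0.14 + 0.64) | 17.9% | -2.1 |
| 40% | 0.12/(0.12 + 0.64) | 15.8% | -4.2 |
| 50% | 0.10/(0.10 + 0.64) | 13.5% | -6.5 |

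With 25% drop-out elsewhere and 10%, 40% or 50% in Essure women with the event, the same formula gives +0.9, -1.0 and -1.6 points at p = 5%; +1.8, -1.8 and -3.1 at p = 10%; and +3.1, -3.3 and -5.7 at p = 20%.

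**Would a balance check reveal it?** A simulation used 300 runs, about 350 Essure women, about 2:1 allocation, true difference 0, risk about 11-12%, and 25% drop-out elsewhere.

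- The enrollment-time match gave a difference of 0.0 points when all outcomes were observed.
- Re-matching among retained women gave +1.7, -0.1, -2.0 and -3.6 points for event-related Essure drop-out of 10%, 25%, 40% and 50%.
- Pairs fell from about 333 to between 242 and 254. About 20% of the women in the new set were not in the first one.
- The largest baseline mean difference averaged about 0.04 SD, so balance looked good while the estimate was biased.

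**The case against.** The strongest reply is that the SAP never says leavers are removed. A reader might infer that the plan prescribes a completers-only match, but the text does not support that. SAP 7 still defines the Adjusted FAS by attempted procedure, SAP 4.3 keeps leavers in the analysis populations, and SAP 4.6.2 uses data up to withdrawal. The protocol wording, which is later than the version the SAP lists, speaks only of balance. This stands, and the point is therefore conditional. But the drop-out rationale in SAP 7 has no other way to operate on fixed data, so the sentence conflicts with the rest of the plan.

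A reader might also infer that the match could be steered by interim results. The safeguards weigh against that. The matching party sees only baseline data and group, its decisions are documented, and of its proposal SAP 4.5.1 says: "This proposal will subsequently be discussed with the FDA". These protections are real, but they do not stop selection through who remains. A drop-out-driven match would also need retention data that the access rule withholds.

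Third, a reader might infer that Essure women with pain or device removal are in fact lost more often, so that the bias favors Essure. The documents give no drop-out data, and Protocol 9.6.1.6 keeps women with surgery or removal in follow-up. The direction is unknown.

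Finally, the study is exploratory and the interims make no formal comparison, so this is not a type I error problem. The unadjusted FAS is reported alongside and re-matching does not touch it. A gap between the two sets would be visible, although confounding could also explain it.

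**Conclusion.** The concern holds as a gap and an internal conflict in the rules for the primary set. The documents allow the match to be repeated or re-evaluated late without a trigger or a defined pool, and the SAP's stated reason can take effect only by selecting on retention. If that were done, the illustrated bias runs from +2.0 to -6.5 points at an assumed 20% risk with 20% drop-out elsewhere, and is smaller at lower risks. It is zero if drop-out is unrelated to the event within arm. Size and sign rest wholly on assumed rates. What does not depend on them is that the primary set is not fixed across reports and that a good balance table would not rule the bias out.

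**What to change.** Delete the repeat-matching sentence from SAP 7. State instead that the matched Adjusted FAS is built once from the baseline data of all FAS women, locked before the first interim, and used for every interim and final analysis, with no woman added or removed for later drop-out.

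Keep the 3-year and end-of-study balance checks among women still followed, as descriptive diagnostics of attrition. Label any re-match as a sensitivity analysis. Align SAP 7 with Protocol 10.5 and update the protocol versions listed in SAP 1.2.

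A censoring-weighted sensitivity analysis within the locked set is optional. Locking stops selection through re-matching but does not itself deal with informative censoring, and SAP 6.8 addresses only the defined censoring events.

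The cost is SAP wording and a short protocol clarification, with no new data. The small downside is that balance among women still followed may drift, and the drift would be reported, not corrected by re-matching.
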